Relevant data were retrospectively collected, including demographics [i.e., sex, gestational age, age at admission, birth weight (BW)], perinatal factors [i.e., pregnancy induced hypertension (PIH), CAM, cesarean section, prenatal glucocorticoid administration, respiratory distress syndrome (RDS), sepsis, PDA, 5-min Apgar score], management during hospitalization [i.e., surfactant administration, noninvasive and invasive mechanical ventilation (IMV), postnatal

glucocorticoid administration, packed red blood cell (PRBC) transfusion], complications during hospitalization [i.e., IVH, retinopathy of prematurity (ROP), NEC], and outcomes. Primary outcomes were the severity of BPD, HOT at discharge, and mortality between 28 days after birth and 2 years of age. Secondary outcomes were (1) duration of hospital stay; (2) duration of oxygen supplementation; (3) routine physical assessment; (4) wheezing disorders; and (5) clinical visits and rehospitalizations for a respiratory reason between discharge and follow-up. The long-term outcomes were evaluated until 2 years of age.

Statistical Analysis

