Statistical analysis was performed using SPSS 26.0. We used the Shapiro-Wilk test to analyze the normality of the data distribution. Variables without normal distributions were analyzed using the Wilcoxon-Mann-Whitney test and are reported as medians [interquartile ranges (IQRs)]. All normally distributed variables were analyzed using a t-test for comparisons of two independent groups and are presented as the means \pm standard deviations. Categorical variables were analyzed using the chi-square test or Fisher's exact tests and are reported as the numbers (%) of subjects. To further evaluate the associations between typical chest imaging findings and the primary and secondary outcomes, a propensity score analysis with 1:1 matching was performed. The following covariates were included based on previous studies: GA, BW, cesarean section, CAM, PIH, sepsis, RDS, PDA, prenatal glucocorticoid administration, postnatal glucocorticoid administration, NEC, IVH, RSD, IMV \geq 7 days, \geq 2 PRBC transfusions. The nearest neighbor matching method was used to select each matched pair by using calipers with a width equal to 0.01 of the standard deviation of the logit of the propensity score. Typical chest imaging findings and the above 15 covariates were analyzed for collinearity and incorporated into the multivariate binary regression model, and the forward likelihood ratio (LR) was used to select the variables to further determine the independent factors of BPD infant mortality. A p-value < 0.05 was considered statistically significant.

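### For HOT at discharge and BPD severity the only confounder-adjusted result planned comes from 1:1 matched pairs; full-cohort models for both would be a cheap gain in precision

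*Combined protocol and SAP*

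**What the plan says.** The outcome definitions, just before the Statistical Analysis section, name three primary outcomes: "Primary outcomes were the severity of BPD, HOT at discharge, and mortality between 28 days after birth and 2 years of age".

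The Statistical Analysis section then describes three layers of analysis.

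- **Unadjusted two-group tests.** For categorical data: "Categorical variables were analyzed using the chi-square test or Fisher's exact tests and are reported as the numbers (%) of subjects". t-tests and Wilcoxon-Mann-Whitney tests cover the other variables. None of these is limited to matched infants.
- **Matching, for all primary and secondary outcomes.** "To further evaluate the associations between typical chest imaging findings and the primary and secondary outcomes, a propensity score analysis with 1:1 matching was performed". Pairs are formed by nearest neighbour, with "calipers with a width equal to 0.01 of the standard deviation of the logit of the propensity score".
- **One regression.** "Typical chest imaging findings and the above 15 covariates were analyzed for collinearity and incorporated into the multivariate binary regression model". The sentence continues: "the forward likelihood ratio (LR) was used to select the variables to further determine the independent factors of BPD infant mortality". The section does not say whether this model uses the whole cohort or the matched pairs.

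No regression, weighting or other full-cohort adjusted analysis is described for HOT or severity. The documents give no cohort size, share of infants with typical imaging, expected number of pairs, event rate or power.

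**The concern.** The plan adjusts for 15 covariates because it does not regard the crude comparison as enough. For two of its three primary outcomes that adjustment happens only inside the matched pairs. One-to-one matching keeps at most one comparator per typical-imaging infant and drops every infant without a partner inside the caliper, including typical-imaging infants, the group the study hypothesis is about.

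The covariates are needed for every infant to fit the propensity score, so full-cohort models for HOT and severity need no new data. Without them, a non-significant matched result for either outcome could reflect discarded infants as easily as absence of association, and the reader would have no adjusted full-cohort estimate to compare it with.

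**Working it through.** The plan states no sample size, power or pair count, so there is no figure of its own to reproduce. All cohort inputs below are assumed. The caliper, the 1:1 ratio, the number of covariates and the 0.05 level come from the Statistical Analysis section ("A p-value < 0.05 was considered statistically significant"; two-sided testing is assumed).

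**1. Closed form.** Let n be the number of typical-imaging infants, r the ratio of other infants to them, and f the fraction matched.

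- Full-cohort variance of a difference is proportional to 1/n + 1/(rn) = (1 + 1/r)/n.
- Matched variance is proportional to 2/(fn).
- Precision retained by matching = f(1 + 1/r)/2.

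With r = 2 this is 0.75 at f = 1, 0.45 at f = 0.6 and 0.30 at f = 0.4. More than half is lost only if f < r/(1 + r): below 50% matched at r = 1, 67% at r = 2 and 75% at r = 3. This flatters the full cohort, because adjusted regression pays for the correlation between imaging and covariates. With an assumed variance inflation of 1.33, the 0.45 becomes 0.45 × 1.33 = 0.60.

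**2. What this means for power.** Assume HOT in 60% v 40%, 100 typical-imaging infants and r = 2. Power = Φ[(0.20 − 1.96·SE0)/SE1], with SE0 from the pooled proportion and SE1 from the separate ones.

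- 60 pairs: SE0 = √(0.50/60) = 0.0913, SE1 = √(0.48/60) = 0.0894, power 0.59.
- 40, 80 and 100 pairs: 0.43, 0.72 and 0.81.
- Full cohort, 100 v 200, unadjusted: 0.91. This is an upper guide, since adjustment costs some precision.

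**3. Simulation of precision.** Assumed: 15 covariates; imaging share set at 25%, 33% or 50% (25% or 50% at N of 800 and above); confounding of 0.5 or 1.0 log-odds per SD of the covariate score; a binary outcome with log-odds −0.4 + 0.6 per SD + 0.8 for imaging (conditional OR e^0.8 = 2.23). Greedy 1:1 matching is compared with full-cohort logistic regression standardised to the typical-imaging infants, with 150 to 200 replicates per scenario. Precision retained = variance(regression)/variance(matched), on the risk-difference scale.

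| N | Fraction matched, 0.01 SD | Precision retained, 0.01 SD | Precision retained, 0.2 SD |
|---|---|---|---|
| 150 | 0.24–0.37 | 0.27–0.33 | 0.68–0.76 |
| 250 | 0.32–0.51 | 0.36–0.41 | 0.66–0.81 |
| 400 | 0.41–0.64 | 0.43–0.55 | 0.69–0.92 |
| 800 | 0.52–0.80 | 0.53–0.63 | not run |
| 1500 | 0.58–0.88 | 0.58–0.71 | not run |

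The loss at the planned caliper is therefore 59–73% at N = 150–250, 45–57% at N = 400 and 29–47% at N = 800–1500.

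**4. Simulation of power for HOT.** Assumed: 30% typical imaging, HOT about 25%, conditional OR 2.5, two strengths of confounding, 400 cohorts per scenario.

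| N | Matched, 0.01 SD | Matched, 0.2 SD | Full-cohort regression |
|---|---|---|---|
| 250 | 30–32% | 53–54% | 74–78% |
| 400 | 57% | 74–79% | 90–92% |

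The matched variance is 2.2–3.3 times that of regression at 0.01 SD and 1.5–1.7 times at 0.2 SD. With no imaging effect, the regression's mean risk difference was −0.004 to 0.001 and its type I error 4–7%.

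A separate run, also on assumed inputs, gave 34% v 75% at N = 250 and 64% v 94% at N = 400 (planned matching v regression), type I error near 6% for the regression, and a variance ratio of about 1.4–1.5 at N = 800. For N = 800 the table in step 3 implies 1/0.63 = 1.6 to 1/0.53 = 1.9. The size depends on the inputs; the direction does not change.

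**The case against.** Four stronger readings are tempting, and the documents do not support them.

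- **That HOT and severity rest on the matched subset alone.** Unadjusted tests outside the matching are also described. Only the adjusted inference rests on the pairs.
- **That most of the precision is lost.** No cohort size or matched fraction is given, and in the simulations the loss falls below half at N of 800 or more.
- **That a real difference is likely to be missed.** At N = 400 the planned matching still has 57% power under the step 4 inputs. Severity was not computed at all.
- **That mortality is assured the full-cohort adjusted estimate the others lack.** The regression's analysis set is unstated, and forward selection can drop the imaging term.

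Much of the gap also belongs to the caliper. In step 4, moving to 0.2 SD closes about half of it at N = 250 and more than half at N = 400. Any separate criticism of the caliper should not count that part again. A loss does remain at 0.2 SD.

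The regression has weaknesses of its own. At N = 250 with 25% HOT there are 0.25 × 250 ≈ 62 events for 16 terms, about 4 per term. A check on assumed inputs (500 replicates, true OR 2.5) gave a geometric-mean OR of 2.72 at N = 250 and 2.91 at N = 150, so the estimate drifts away from the null. With an unmodelled quadratic confounder and no imaging effect, type I error reached 27% at N = 250. A linear propensity score might suffer too; that was not compared. The good null behaviour in step 4 therefore holds only when the model form is right.

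Finally, the title announces a propensity score analysis, and matching deliberately gives up precision to compare infants where the groups overlap. Regression brings in unmatched infants by extrapolation and may target a different population or a conditional rather than a marginal effect. Standardising to the typical-imaging infants, as in step 3, narrows that difference but does not remove it. This is a good reason to keep the matched analysis as planned. It is not a reason to leave two primary outcomes without a full-cohort adjusted estimate beside it.

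**Conclusion.** The point holds as a cheap improvement, not as an error that invalidates the plan. That mortality is the only outcome named for the regression, and that HOT and severity have no other adjusted analysis than the matched pairs, follows from the text alone.

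The size is conditional. For a binary outcome such as HOT at the planned caliper, the assumed inputs give a loss of more than half the precision at N of about 250 or less, about half at 400, and less than half at 800 or more. At a 0.2 SD caliper with N = 150–400, the step 3 loss is 8–34% and the step 4 ratios of 1.5–1.7 imply 33–41%. For severity only the direction can be argued. These figures rest on assumed covariate and outcome models and on a regression of the right form.

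**What to change.** Keep the matched analysis as planned and add two supporting models on all eligible infants:

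- **HOT at discharge:** logistic regression on typical imaging and the same pre-specified covariates.
- **BPD severity:** a proportional-odds model with the same terms and a stated check of proportionality.

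Force imaging and the covariates in, without forward selection, and use a penalised fit if events are few for the number of terms. The covariate listed as RSD, beside RDS, needs defining first. For each outcome, report the adjusted imaging effect with its 95% CI next to the matched estimate, label the regression as supporting, and state which infants and which effect each estimate refers to. Also state the analysis set of the mortality regression.

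The cost is two further models on data already collected. The downside is dependence on the outcome model form and a possible difference in target population or effect, so the two estimates may legitimately differ and both should be shown.

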Official title Clinical Characteristics and Outcomes Until 2 Years of Age in Preterm Infants With Typical Chest Imaging Findings of Bronchopulmonary Dysplasia: A Propensity Score Analysis

NCT number 04163822

Document date 2021.5.18

Bronchopulmonary dysplasia (BPD) is a common chronic respiratory disease in preterm infants. The increase in the survival rate of premature babies following the improvement of perinatal treatment and care has caused an increase in the incidence of BPD in recent years, which has seriously affected the quality of life of preterm infants. According to the consensus reached at the workshop sponsored by the National Institute of Child Health and Human Development (NICHD) in 2001, BPD was clinically defined based on oxygen dependency in preterm infants. However, the refined NICHD definition of BPD in 2018 emphasized imaging findings to support a diagnosis of lung parenchyma disease.

Fibrotic opacities and cystic changes on chest imaging [chest X-ray (CXR) or computed tomography (CT) scan] were considered typical findings in BPD patients. In patients with severe BPD, the presence of bubbles/cystic appearance on CXR after 28 days of life was reported to be an important factor, and typical imaging findings can predict a poor pulmonary outcome in BPD patients. BPD is associated with poor outcomes. Although many studies have been conducted on BPD, there are limited reports specifically evaluating the association of typical imaging findings with clinical characteristics and later outcomes in patients with BPD.

We hypothesized that BPD with typical imaging findings was likely to be a particular subgroup of this entity, with a unique etiology, clinical characteristics and prognosis. Therefore, we performed a retrospective cohort study using data from the Department of Neonatology, Children's Hospital of Chongqing Medical University (CHCMU), and the patients were followed by telephone. Eligible patients fulfilled the following three criteria simultaneously: (1) BPD diagnosis according to the 2001 NICHD consensus; (2) chest imaging examination (CXR or CT) in the first week after birth; and (3) hospitalization within the first 7 days after birth. Patients were excluded from the study if they met one of the following conditions: (1) major congenital malformations or laboratory-confirmed chromosomal abnormalities; (2) inadequate clinical data or missing chest imaging data; or (3) loss to follow-up.

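### The forward-LR mortality regression does not force in the imaging finding, so it may give no odds ratio for the study exposure, or one exaggerated on average unless power is high

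*Combined protocol and SAP*

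**What the plan says.** The Statistical Analysis section describes two adjusted analyses that bear on mortality.

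- **Matching.** To evaluate the "associations between typical chest imaging findings and the primary and secondary outcomes, a propensity score analysis with 1:1 matching was performed". Imaging status defines the matched groups.
- **Regression.** "Typical chest imaging findings and the above 15 covariates were analyzed for collinearity and incorporated into the multivariate binary regression model", after which "the forward likelihood ratio (LR) was used to select the variables to further determine the independent factors of BPD infant mortality". No variable is named as forced or retained, and entry and removal levels are not given. The only threshold in the section is "A p-value < 0.05 was considered statistically significant".

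The outcomes paragraph says: "Primary outcomes were the severity of BPD, HOT at discharge, and mortality between 28 days after birth and 2 years of age". The opening hypothesis is that "BPD with typical imaging findings was likely to be a particular subgroup of this entity, with a unique etiology, clinical characteristics and prognosis".

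**The concern.** The study exposure is treated as one of 16 candidates (imaging plus 15 covariates) in a data-driven search on a primary outcome. Saying that the terms are incorporated might suggest that all of them stay in the model, but the same sentence then has forward LR choose among them.

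There are two possible results, and neither is a sound estimate of the exposure effect:

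- **Imaging is not selected.** The regression gives no imaging OR or confidence interval. A reader may take this as evidence of no association when deaths may simply be few.
- **Imaging is selected.** Its OR is seen only because it was significant, so it overstates the truth on average unless power is high. Confounders that missed entry are also left out, which moves the OR up or down with the direction of confounding. Omitted negative confounding can offset the exaggeration.

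The hypothesis concerns prognosis, so readers are likely to set this regression beside the matched mortality result. The plan does not commit to reporting an imaging OR whatever its p-value.

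**Working it through.** **Inputs from the plan.** There are 16 candidates, forward-LR selection and a 0.05 significance level. The plan states no sample size, deaths, exposure prevalence, effect size or power, so there is no figure to reproduce, and every result below rests on assumed inputs.

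**Step 1: effect of reporting only when significant (no confounding, two-sided 0.05).** Let Z ~ N(d, 1), where d is the true log OR divided by its standard error. Power is P = Φ(d − 1.96) + Φ(−d − 1.96). The average exaggeration of the log OR is

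E[Z given |Z| > 1.96] / d = [d·P + φ(d − 1.96) − φ(d + 1.96)] / (P·d).

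At 50% power d = 1.96, giving (0.98 + 0.3989 − 0.0002) / 0.98 = 1.407. A true OR of 2 then reads 2^1.407 = 2.65.

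| Power | d | Factor on log OR | True OR 2 reads |
|---|---|---|---|
| 30% | 1.435 | 1.805 | 3.49 |
| 50% | 1.960 | 1.407 | 2.65 |
| 80% | 2.802 | 1.125 | 2.18 |
| 95% | 3.605 | 1.030 | 2.04 |

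**Step 2: deaths needed for 80% power at OR 2 (unadjusted 2×2 Wald test).** With exposure e and risks p1 (exposed) and p0 (unexposed), V = 1/(e·p1) + 1/(e(1 − p1)) + 1/((1 − e)p0) + 1/((1 − e)(1 − p0)), and N = (2.802 / ln 2)²·V. Example: for 12% mortality and 35% exposure, p0 = 0.0930, p1 = 0.1702 and V = 38.47. Then N = 16.34 × 38.47 ≈ 629, or about 75 deaths.

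| Mortality | Exposure 20% | 35% | 50% |
|---|---|---|---|
| 8% | 84 | 72 | 78 |
| 12% | 91 | 75 | 81 |
| 17% | 100 | 81 | 84 |

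**Step 3: simulation of the selection rule.** There were 500 replicates per case. Assumptions:

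- exposure 35%; 15 covariates (2 continuous, 13 binary) sharing a severity factor
- outcome log ORs 0 to 0.6; exposure log ORs +0.5, 0 or −0.5 times these (positive, no or negative confounding)
- entry at p < 0.05 (score test), removal at p > 0.10 (LR)

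Results for true OR 2, in the order positive / none / negative confounding:

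| N, mortality (deaths = N × rate) | Imaging dropped, % | Median OR when kept | Forced in + all 15 covariates, Firth-penalised, always reported |
|---|---|---|---|
| 250, 8% (20) | 66.4 / 74.2 / 84.6 | 4.78 / 4.61 / 4.94 | 1.94 / 1.94 / 2.01 |
| 250, 12% (30) | 55.6 / 66.6 / 77.8 | 3.63 / 3.56 / 3.92 | 2.02 / 2.00 / 2.03 |
| 400, 12% (48) | 44.8 / 49.8 / 67.4 | 2.82 / 2.66 / 2.99 | 1.97 / 2.04 / 2.00 |
| 500, 12% (60) | 38.4 / 38.8 / 58.6 | 2.61 / 2.47 / 2.63 | 1.94 / 2.02 / 2.07 |

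Confidence-interval coverage was 79–94% when imaging was kept by selection and 94–96% for the forced, penalised model.

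**Step 4: where the distortion comes from.** Forcing imaging in but still choosing covariates by forward LR, all results reported, gives medians of 2.19–2.56 with positive and 1.69–1.90 with negative confounding, so forcing alone is not enough. Restricted to significant results, forced and unforced forward selection agree within about 3% at 30 or more deaths and within 3–10% at 20. The causes are therefore the significance filter and the omitted confounders, not the entry algorithm itself.

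**Step 5: where the problem is small.** With true OR 3 and 17% mortality (N = 600 and 1,000; 102 to 171 deaths), imaging is dropped in 0–7%. The kept OR is 3.17–3.31 (positive), 3.03–3.06 (none) and 2.88–2.94 (negative confounding). With no true effect (N = 400, 12% mortality), imaging is kept in 5.0–5.8% (standard error 1.0 point), so there is no clear excess of false positives.

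**Step 6: sensitivity to the simulation set-up.** A separately coded simulation used 40% exposure, covariates correlated 0.2 and 5 of them prognostic. At true OR 2 and about 45 deaths, imaging was retained in 52–56% of runs with zero or positive confounding (OR when retained 2.9–3.4) and in 32% with negative confounding (OR 3.2). At about 91 deaths the figures were 72–76% (2.3–2.4) and 63% (2.4).

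**The case against.** The strongest reply is that the plan gives the exposure question to another analysis. The matched comparison covers all primary and secondary outcomes, including mortality, and cannot drop imaging. The regression has a different stated aim, a search for independent factors, and treating imaging as one candidate suits that aim. Nothing in the documents says that non-selection will be read as no association. This stands as a limit on scope: the exposure–mortality question is not left unanswered.

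The size is also unknown. The larger figures come from 20 to 60 deaths, fewer than the 72 to 100 needed for 80% power at OR 2, and the problem is minor when power is high. This stands too.

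The contrast between 2.47–4.94 and 1.94–2.07 also changes two things besides forcing: it sets significant-only against all results, and it adds penalisation. That is fair. In the second simulation, an unpenalised model with all 16 terms gave medians of 2.3–2.5 at about 20 deaths, about 2.3 at about 45 and 2.1 at about 91, so forcing without penalisation leaves sparse-data bias.

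None of this removes the defect. As written, a second analysis of a primary outcome can lose the exposure estimate or show it only when it is significant.

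**Conclusion.** The concern holds. Followed as written, the regression may report no imaging OR, or one exaggerated on average unless power is high. The mechanism is certain from the text. Its size in this study is not, because the number of deaths, the effect size and the direction of confounding are not stated. Under the assumptions above it ranges from severe (true OR 2 and about 20 deaths: dropped in 66–85%, kept OR 4.6–4.9) to negligible (true OR 3 and more than 100 deaths). It does not undermine the matched mortality comparison. It is a cheap improvement that should be made. Use of 0.05 for entry and 0.10 for removal is an assumption, since the plan states neither.

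**What to change.** Add one mortality model with typical imaging findings forced in.

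- Adjust by the propensity score, or by a covariate set fixed without reference to the outcome data, penalised if deaths are few. Do not choose these covariates by forward LR.
- State which covariates precede the imaging finding, since some are in-hospital management or "complications during hospitalization [i.e., IVH, retinopathy of prematurity (ROP), NEC], and outcomes".
- Report the imaging OR and 95% confidence interval whatever the p-value, beside the matched result. Label the model post hoc if outcomes have already been analysed.
- Keep the forward-LR list as exploratory, state entry and removal levels, and say that non-selection is not evidence of no association.

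The cost is SAP wording and one model on the same data. The OR will probably be less striking, and there will be no confirmatory list of independent factors. The adjustment method must be named in advance, because the two options estimate different quantities: at true OR 2 the propensity-score-adjusted median was 1.72–1.96 (marginal OR 1.71–1.76), against 1.94–2.07 with all 15 covariates. A small set that omits confounders leaves bias: six fixed covariates gave 1.71–2.25.
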